Thus, good evidence suggests that at least acute treatment with ARBs could ameliorate lung injury in COVID-19. We therefore propose to test losartan in a Phase I proof of concept and safety trial. The primary hypothesis to be tested is that losartan treatment is safe in the setting of acute SARS-CoV-2 infection. Secondarily, losartan can potentially reduce the length of respiratory failure due to SARS-CoV-2.

Significance

Importance of the problem: As outlined above, there is currently no data that supports specific treatment options for respiratory failure in COVID-19. There are active or soon to be active clinical trials that may show promise in this space such as blocking IL-6 with tocilizumab²⁰ or using hydroxychloroquine. None of these therapies are without side effects and alternative or additional approaches could lessen the burden of respiratory failure in this patient population.

Approach and Protocol

This is an open label, phase 1 clinical trial to evaluate the safety of losartan in respiratory failure due to COVID-19.

Clinical Trial setup:

Detailed inclusion and exclusion criteria are listed below. Briefly, 50 patients with COVID-19 and respiratory failure who meet criteria and agree to participation in the study will be placed on losartan 25 mg daily on study day 0. If parameters are met the dose of losartan will be increased to 50 mg on study day 3. Participants will continue losartan until they experience resolution of respiratory failure (normal oxygen levels on room air), are discharged from the hospital, meet stoppage criteria (detailed below) or complete 14 days of therapy.

Primary hypothesis and endpoint:

- Losartan is safe in acute respiratory failure due to SARS-CoV-2.

Secondary endpoints:

- Losartan reduces the number of days on supplemental oxygen in respiratory failure due to COVID-19
- Incidence of mechanical ventilation use
- Days on mechanical ventilation
- Incidence of non-invasive positive pressure ventilation or heated high flow nasal cannula use
- Days on non-invasive positive pressure ventilation or high flow nasal cannula
- Incidence of transfer to ICU from non-ICU hospital bed
- ICU length of stay (days)
- In-hospital mortality
- Hospital length of stay (days)
- Cumulative incidence of severe adverse events
- Cumulative incidence of adverse events
- Change from baseline in oxygenation

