Patients and/or surrogate decision maker who do not give consent to treatment will be asked to allow collection of data from their medical record for use as a control group. Patients or surrogate decision makers who cannot consent in person, will be consented in accordance to the KUMC remote consent guidelines.

Parameters to be collected:

General: Demographics, clinical symptoms, history of other medical conditions, routine blood work, and concomitant medications. Baseline characteristics will include age, sex, race, ethnicity and body mass index, Simplified Acute Physiology Score (SAPS) II, National Early Warning Signs (NEWS), Sequential Organ Failure Assessment (SOFA) and acute physiology and chronic health evaluation (APACHE) II. The APACHE II will be collected only for participants admitted in the ICU.

Physical examination: We will record vital signs such as highest and lowest temperatures (°C), highest respiratory rate, highest heart rate, lowest mean arterial pressure (mmHg), highest oxygen requirements and body mass index (BMI).

Confirmation of infection with SARS-CoV-2 by PCR testing by chart. Also, documentation of other infections if present.

Blood samples: We will collect laboratory values throughout the study (hemoglobin, platelet count, white blood cell count, lymphocyte count, liver enzymes, glucose, blood urea nitrogen, creatinine, creatine kinase, lactate, and arterial blood gas) and as indicated (LDH, ferritin, troponin), potassium and other values available in EMR. Store plasma at beginning and at the end of study for later analysis (possibly IL-6 etc.).

Nasopharyngeal swabs: We will collect nasopharyngeal swabs at study enrollment and end of study to determine SARS-CoV-2 viral load by quantitative PCR.

Radiographic imaging will be recorded upon presentation and subsequently thereafter as indicated.

Monitor for deteriorating acute respiratory failure and determine the indication the need for mechanical ventilation.

Study procedures (see schematic)

Day 0

- Labs collected for routine clinical care and the medical record will be reviewed to screen for eligibility. Assuring pre-menopausal women have a negative pregnancy test.
- Consenting participants who meet enrollment criteria will be started on losartan 25 mg once daily per mouth.
- Treatment group will have nasopharyngeal swab and research plasma collected for analysis.
- Control group will be followed only for data collection until study completion.

Day 1-2:

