Patients that request to not be treated with Losartan will be approached by the study team to request permission for their standard of care treatment and data be followed and recorded by the research team for this study. Patients that agree, will sign the consent form, but will not provide a blood sample for research. We will also collect medical information relating to safety criteria on historical controls treated at the University of Kansas Hospital in the 30 days prior to the study start date (3/25/2020) and during the study period. These controls will be retrospectively identified through query of the electronic health record. We will attempt to include controls that meet all criteria for enrollment into the study but to achieve a ratio of controls to study participants of 2:1 may need include some with exclusion criteria (excluding prior ACE inhibitor or ARB use). Controls identified retrospectively will not undergo informed consent as this represents minimal risk.

Losartan

Losartan is an FDA-approved ARB widely prescribed for treatment of hypertension, heart failure, and for renal protection in patients with diabetes. The doses proposed in this study are well tolerated by non-hypertensive patients without significant effect on blood pressure. The proposed starting dose of losartan is 25 mg orally per day with increase to 50 mg orally per day on day 3 if tolerated until they patient is discharged from the hospital, met stoppage criteria (above) or completed 14 days of therapy.

The most common side effects are fatigue and dizziness. Serious adverse events that are rare include angioedema, hypotension, renal dysfunction or failure, blood dyscrasias, hepatitis, or rhabdomyolysis. The following are meant to mitigate risk to the subjects: Dosing will be done in an inpatient setting with clinically indicated close observations of blood pressure and organ dysfunction (blood work). Subjects with hyperkalemia, renal dysfunction, or who are taking potassium supplements will not be enrolled into the study. Participants will be given written descriptions of potential side effects and potential responses to the side effects.

Sample size and Statistics

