Since there is no information on the effects of losartan in human beings suffering from COVID-19, a statistical analysis based on efficacy is not possible. From a safety perspective, we would accept considering losartan equivalent or superior to the comparison group not receiving losartan (historical or no consent) if there is a $\pm 20\%$ difference in total AE/SAEs. Historical controls will be matched with study participants based on upon age, sex and disease severity in a 2:1 ratio for safety comparison. From a safety perspective, losartan's long track record as a safe medication is reassuring. See section on DSMB for further details on safety monitoring and analysis.

Confidentiality

All information provided by the subject to the investigators, and all information that is collected about the subjects by the investigators, shall be kept confidential to the extent that is provided by law. Computer data files will be stored and backup up to secure, HIPPA compliant, password protected computers and servers. Electronic data capture into REDCap system will be used. Access to these databases will be restricted to individuals associated with the study who require access to the data to perform their duties. These individuals will be named by the principal investigator prior to initiation of the clinical trial. The subject's actual identity cannot be ascertained exclusively from these data and the subject's name shall not be used in any publications. All investigators and staff involved in the research protocol will be bound by this agreement of confidentiality.

Adverse Event and Serious Adverse Event Documentation

Definition of an Adverse Event

For the purpose of this protocol, an AE will be defined as any untoward medical occurrence in a subject during the study listed under DMSB - Anticipated Adverse Events and Grading Scale section of this protocol as well as safety monitoring data listed on table 1 as well as stoppage criteria for losartan.

The event does not necessarily have a causal relationship with the treatment. AEs will be collected for both study groups, treatment and control from the time the ICF is signed until the subject completes study participation.

Definition of a Serious Adverse Event

An SAE is any AE that meets any of the following outcomes:

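### The safety comparison with non-randomised controls names no severity measure for matching and plans no adjustment for the baseline values that drive the counted adverse events

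*Combined protocol and SAP*

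**What the plan says.** Sample size and Statistics accepts losartan as equivalent or superior to patients not receiving it "if there is a $\pm 20\%$ difference in total AE/SAEs". The scale (absolute or relative), the unit of analysis and the statistical method are not given. The comparison group has two sources, historical controls and patients who declined losartan. The matching statement covers only the first: historical controls are to be "matched with study participants based on upon age, sex and disease severity", two per participant. The section refers the reader to the DSMB section for further safety analysis. That section has grading, reporting and meeting rules, but no model, stratification, weighting or use of matched sets.

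Parameters to be collected lists SAPS II, NEWS and SOFA as baseline characteristics. It restricts only one score: "The APACHE II will be collected only for participants admitted in the ICU". The same section lists creatinine, potassium, lowest mean arterial pressure (MAP) and highest oxygen requirement. For record-based controls, the Control section says "We will also collect medical information relating to safety criteria on historical controls", found by a query of the electronic record.

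Definition of an Adverse Event ties AEs to the anticipated losartan effects, the Table 1 monitoring values and the losartan stoppage criteria.

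**The concern.** Losartan patients agreed to treatment. Controls either declined it or were found in the record. Nothing balances the groups except matching on three variables, one of them undefined, and for decliners not even that.

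The counted events are largely changes in creatinine, potassium, blood pressure, liver enzymes and blood counts. The value on the first day is an obvious predictor of each. If the groups differ at the start in kidney function, potassium, blood pressure or respiratory support, that difference becomes part of the apparent drug effect. It can hide harm or create it, and the conclusion at stake is the trial's primary one. Because no analysis method is fixed, the choice between an adjusted and an unadjusted comparison also stays open until the data are seen.

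**Working it through.** **Plan's own figure.** There is none to reproduce. The document gives 50 treated patients and a 2:1 control ratio, hence 2 × 50 = 100 historical controls, but no AE rate, alpha or power.

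**Step 1: can an eligible patient be near or past an AE threshold on Day 0?** Eligibility limits against AE thresholds:

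| Measure | Inclusion/Exclusion criteria | Table 1 or stoppage criteria | Eligible patient on Day 0 |
|---|---|---|---|
| Potassium | excluded only above 5.5 mM | Grade 1 from ULN to 5.5 mmol/L | may already be in Grade 1 range |
| Renal function | excluded below Cockcroft-Gault 30 | Grade 1 from creatinine above ULN; stoppage below 30 | may be above ULN, or just above the stoppage limit |
| Liver enzymes | excluded above 5 × ULN | Grades 1 and 2 run up to 5 × ULN | may already be in Grade 1 or 2 range |
| Blood pressure | excluded below 90 systolic or 60 diastolic, or norepinephrine above 0.1 | stoppage at the same limits | may be just above them, or already on norepinephrine |
| Hemoglobin, leukocytes, platelets | no limit | Grade 1 from below LLN | may be in a graded range |
| Respiratory support | from tachypnea alone to mechanical ventilation | separate hypotension scale for sedated, ventilated ICU patients | may fall on either scale |

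The plan does not say whether a value already past a threshold on Day 0 is counted. If it is, baseline status is the event. If it is not, a patient close to the threshold is still more likely to cross it.

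**Step 2: size of the shift (all inputs assumed).** Take one binary factor, abnormal baseline creatinine, a drug with no effect, and as outcome the proportion of patients with a qualifying AE.

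Shift = (prevalence in losartan group − prevalence in controls) × (AE risk with factor − AE risk without).

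With risks of 80% and 40%:

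- Prevalence 20% against 40%: losartan 0.2 × 0.8 + 0.8 × 0.4 = 0.48; controls 0.4 × 0.8 + 0.6 × 0.4 = 0.56; difference −8 points.
- Prevalence 20% against 30%: controls 0.3 × 0.8 + 0.7 × 0.4 = 0.52; difference 0.48 − 0.52 = −4 points.

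If ±20% means absolute points, these are 8/20 = 40% and 4/20 = 20% of the margin.

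**Step 3: range.** With risk differences of 20 to 50 points and imbalances of 10 to 40 points, the shift runs from 0.1 × 0.2 = 2 points to 0.4 × 0.5 = 20 points. The sign follows the imbalance and can go either way.

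**Step 4: against sampling error.** At 50 and 100 patients, ignoring matching, the standard error for 0.48 against 0.56 is √(0.48 × 0.52/50 + 0.56 × 0.44/100) = 0.086. The 8-point shift is 0.08/0.086 = 0.93 standard errors. For 0.48 against 0.52 the standard error is 0.087, and 4 points is 0.46 standard errors. More patients would not remove the shift.

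**Step 5: what adjustment does here.** Within the abnormal stratum the difference is 80% − 80% = 0, and within the normal stratum 40% − 40% = 0. A comparison that conditions on baseline creatinine returns 0 in both scenarios.

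**The case against.** The plan does not say that the comparison will be unadjusted or that matched sets will be ignored. A reader might infer both, but the text gives no method at all. What can be said is that adjustment is not specified.

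A reader might also take the APACHE II restriction to mean that no severity score covers ward and ICU patients alike. The document does not support that: SAPS II, NEWS and SOFA are listed at baseline without an ICU limit. The gap is that none is named as the matching variable. If SOFA or SAPS II were used, matching would already cover part of creatinine, blood pressure and oxygenation.

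Full eligibility narrows the baseline range, because Cockcroft-Gault below 30, potassium above 5.5 and low blood pressure are excluded. That limits the plausible imbalance, though the table shows it does not remove it. The Control section does let in controls with exclusion criteria if needed to reach 2:1, which could produce larger shifts. That is a separate matter, and the 4-to-8-point illustration does not rely on it.

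Finally, 50 treated patients cannot support a long covariate list, and adjustment for unbalanced confounders may widen the interval. Both objections stand and shape the remedy. A gain in precision should not be claimed.

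**Conclusion.** The point holds in this form: the primary safety conclusion compares non-randomised groups with matching on age, sex and an unnamed severity measure, none stated for decliners, and no pre-specified adjustment. The counted events depend on baseline values that eligible patients can bring with them.

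That baseline imbalance can enter the AE difference follows from the document's own thresholds. The size does not: 4 to 8 points is an illustration resting on assumed risks and prevalences, and on reading ±20% as absolute points. Neither the actual direction nor the actual amount of bias can be known from the plan, and it would go too far to infer that the trial will reach a wrong conclusion. The change should be made before analysis. It is not a reason to stop the trial.

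**What to change.** Amend Sample size and Statistics as follows.

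- **Severity for matching:** index-day SOFA plus respiratory support category (room air, low flow, high flow or non-invasive ventilation, mechanical ventilation).
- **Outcome:** state a patient-level measure that keeps to the plan's AE/SAE total, such as the AE/SAE count per patient, or a grade threshold that not nearly every inpatient meets. Any Grade 1 event would be a poor choice, since Table 1 starts creatinine at any rise above baseline and hemoglobin at any value below LLN.
- **Main safety comparison:** adjusted for a few pre-specified index-day values (creatinine, potassium, lowest MAP, respiratory support), or for one propensity score built from them. SOFA overlaps these and need not be added again.
- **Both control sources:** apply the adjustment to historical and no-consent controls. Account for matched sets where they exist; decliners have none under the current text.
- **Sensitivity analysis:** the unadjusted difference.

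No extra patients or procedures are needed. The work lies in defining an index day for controls, who have no Day 0 dose, and extracting their values for that day. Availability is inferred from the record query and should be checked, SOFA in particular. For patients enrolled after standard-of-care losartan (inclusion criterion 5), the values should predate the first dose. The interval may be slightly wider than the unadjusted one.

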As the name of the virus indicates, death is usually associated with respiratory failure. Thus, the question is how to mitigate the development of lung disease in COVID-19 since no SARS-CoV-2, FDA approved therapeutics are available as yet. While trials with anti-viral and other therapies are being conducted, e.g., remdesivir² and chloroquine³, additional safe and nontoxic therapies to prevent progression of lung disease are needed. We therefore propose a proof of concept clinical trial with **losartan** to block angiotensin II type 1 receptors (AT1R) in the lung of patients with worsening respiratory function due to SARS-CoV-2.

Arguments to use angiotensin receptor blockers (ARBs) for persons with COVID-19 were recently published in at least two opinion pieces.^{4, 5} More importantly the premise is based on scientific data assembled over years in multiple models of viral pneumonia. Like other coronaviruses, SARS-CoV-2 infects cells by binding to angiotensin-converting enzyme 2 (ACE2),^{6, 7} a protein highly expressed in the lung.⁸ The enzyme is thereby downregulated in the setting of viral infection causing dysregulation of the renin-angiotensin axis that results in more angiotensin II⁹ and less angiotensin 1-7, a vasodilator. This finding was confirmed in the systemic circulation of patients with H7N9 influenza in whom elevated plasma angiotensin II is associated with worse outcome.¹⁰ Disproportionate AT1R stimulation has been shown to mediate pulmonary capillary leak and AT1R blockade or knockdown is associated with better outcomes in animal models.^{11, 12} Furthermore, ACE2 null mice develop an angiotensin II-mediated cardiomyopathy through unopposed stimulation of AT1R.¹³

Since AT1R blockade increases ACE2,¹⁴⁻¹⁶ one could be concerned about possibly worsening viral entry with worsening outcome. In this context, hypertension is a risk factor for severe COVID-19 disease and hypertension rates are high in China. However, ARBs are not commonly used in China to treat hypertension.¹⁷ In addition and maybe paradoxically, ACE2 upregulation may still be beneficial in disease models,¹⁸ possibly by increased angiotensin 1-7 production. Interestingly, upregulation of viral binding sites for HIV is also associated with a decrease rather than an increase in HIV virulence.^{5, 19}

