- Monitor subject for safety and losartan stoppage criteria.
- For participants following inclusion criteria #5: Day 0 assessments should be performed on enrollment day as well as day 1 **or** day 2 based on first dose of SOC losartan administration.

Day 3:

- Dose escalation: On study day 3 if none of the parameters listed below are met the dose of losartan will be increased to 50 mg once daily.

Day 4 until study completion:

- Monitor subject for safety and losartan stoppage criteria.
- Treatment group will have nasopharyngeal swab and research plasma collected at end of study.

Stoppage criteria for losartan

- Hyperkalemia (persistent values >5.5 mM recorded on at least 2 readings).
- Worsening renal function (Cockcroft-Gault <30 mL/min/1.73 m²) or urinary output <20 mL/h.
- Skin rashes, palpitations or other moderate or severe adverse events (interference with usual daily activities) without clear explanation should warrant immediate cessation of treatment and notification of study personnel.
- Development of sustained hypotension defined as SBP <90 mmHg, DBP <60 mmHg recorded on at least two readings 30 min apart or use of norepinephrine >0.1 µg/kg/min.

[figure not shown]
- Any change in monitor lab parameters deemed significant and potentially related to study drug by the Investigator.

Dose de-escalation criteria

- Any change in monitoring parameter after dose increase from 25 mg to 50 mg that is considered significant by the investigator will trigger a decrease dose back to 25 mg
- If abnormal parameter is resolved and, in the opinion of the investigator, is unlikely to be related to losartan will increase dose back to 50 mg
- If de-escalation criteria is met after re challenging 50mg dose, the dose will be once more decreased to 25mg until the end of the study.

Criteria for resuming after stopping

- If stoppage criteria have resolved and reason for stoppage is felt to be unlikely or possibly related to losartan, discussion of resumption of losartan with medical monitor
- Dose resumption will start at 25 mg. If stopped at 25 mg → the dose will be continued for three days followed by increase to 50 mg if tolerated. If stopped at 50 mg, 25 mg will be started and escalated to 50 mg the day after if tolerated.

Control

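### Non-fatal COVID-19 respiratory deterioration would not reliably enter the AE/SAE total, which is the only numerical basis for the safety conclusion

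*Combined protocol and SAP*

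**What the plan says.** All references are to the combined protocol and SAP.

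- **AE.** Definition of an Adverse Event limits an AE to "any untoward medical occurrence in a subject during the study listed under DMSB", which points to the section on anticipated events and their grading. Two further sources are then named: the monitoring items in Table 1 and the list of reasons for stopping the drug. The same paragraph group states: "The event does not necessarily have a causal relationship with the treatment". The limit therefore comes from the list, not from attribution.
- **SAE.** Definition of a Serious Adverse Event begins: "An SAE is any AE that meets any of the following outcomes". The first outcome listed is death from any cause during participation.
- **Catch-alls.** Stoppage criteria for losartan include "other moderate or severe adverse events (interference with usual daily activities) without clear explanation", and the anticipated-events section has a near-identical clause. The stoppage criteria also include laboratory changes that the investigator considers significant and possibly drug-related.
- **Decision rule.** Sample size and Statistics accepts losartan as equal to or better than the comparison group on a ±20% "difference in total AE/SAEs". It does not say whether 20% is relative or absolute, or whether events or patients are counted.
- **Primary endpoint.** Safety is the primary hypothesis, with no variable named. AE and SAE incidence, mechanical ventilation, non-invasive or high-flow support, ICU transfer, ECMO, renal replacement and in-hospital mortality are all secondary endpoints.
- **Rationale.** The background notes that, because AT1R blockade raises ACE2, "one could be concerned about possibly worsening viral entry with worsening outcome". It then argues against that concern.

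**The concern.** The trial asks whether losartan is safe in patients who already have COVID-19 respiratory failure. The most direct sign of harm in that population is that respiratory failure gets worse: intubation, escalation of support, or a move to the ICU. If such events are not AEs they cannot be SAEs, and if they are neither they do not enter the quantity on which safety is judged. The secondary endpoints record them but carry no threshold and no role in the rule. The plan could then report losartan as acceptable on safety while more treated patients deteriorate, with no planned step that obliges anyone to set the two results side by side.

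**Working it through.** The plan gives no event rate, alpha or power for its 50 treated patients, so there is no stated figure to reproduce. The main check is a trace of the event through the definitions.

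**Step 1. Is non-fatal respiratory deterioration in any AE source?**

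| Source | Content | Names ventilation, oxygen escalation or ICU transfer for hypoxia? |
|---|---|---|
| Anticipated-events section | Losartan side effects (fatigue, dizziness, angioedema, hypotension, renal, blood, liver and muscle events); catch-all for events without another clear explanation | No |
| Table 1 | Blood counts, angioedema, hypotension, creatinine, potassium, liver enzymes, CPK | No; ICU transfer appears only with platelets, angioedema and hypotension |
| Stoppage criteria | Potassium, renal function, blood pressure, two catch-alls | No |

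**Step 2. Do the catch-alls bring it in?** The clinical ones require that no clear explanation exists. In a patient enrolled for COVID-19 respiratory failure, the disease will usually be taken as the explanation. That is an inference, since the protocol does not say so. The laboratory one could admit a worsening arterial blood gas, which is a collected value. It depends on possible relation to study drug, a test that cannot be applied to untreated controls. Capture by these routes would be a matter of judgement and would differ between groups.

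**Step 3. SAE level.** A non-fatal event that is not an AE is not an SAE, however serious. For fatal events, the opening words require an AE while the first outcome counts death from any cause. The two cannot both be applied literally to a death from respiratory failure.

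**Step 4. Effect on the count.** Assume an excess d of new mechanical ventilation, with all 50 treated patients unventilated at Day 0:

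- d = 0.10: 0.10 × 50 = 5 patients; d = 0.20: 0.20 × 50 = 10 patients.
- Contribution to total AE/SAEs in its own right: 0 on a literal reading, whatever the scale of the ±20%. A patient counts only through death, a listed event or a catch-all.

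**Step 5. Would counting it in a pooled total suffice?** Let *a* be the proportion with a listed event, equal in both groups and independent of respiratory deterioration. The difference in patients with any event is then (1 − *a*) × d.

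- *a* = 0.20: 0.80 × 0.10 = 8 points, and 0.80 × 0.20 = 16 points.
- *a* = 0.40: 0.60 × 0.10 = 6 points, and 0.60 × 0.20 = 12 points.

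All lie inside an absolute 20-point margin, so pooling alone would not expose this excess.

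**Step 6. A larger assumed harm.** Inputs: 50 treated against 100 controls (2 × 50); *a* of 0.20 to 0.40; respiratory deterioration 25 points higher on losartan (10 to 35%, 20 to 45% or 30 to 55%). The rule is read as an observed excess of at most 20 points in patients with any event. Simulation with 400,000 draws per setting gives:

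| Events compared | True difference | Probability that the rule is met |
|---|---|---|
| Listed events only | 0 | 0.992 to 0.998 |
| Listed events and deterioration pooled | 15 to 20 points (0.60 × 25 to 0.80 × 25) | 0.52 to 0.75 |
| Deterioration alone | 25 points | 0.27 to 0.30 |

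Every rate in Steps 4 to 6 is an assumption. The results show direction and mechanism, not an expected size.

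**The case against.** The strongest reply is that the AE definition is not closed. It draws on three sources, needs no causal link, and has catch-alls in two of them. Some deteriorating patients will be counted indirectly: for sedated, ventilated ICU patients, starting vasopressors is already Grade 1 hypotension in Table 1. The SAE text includes any-cause death, and its example of an important medical event, allergic bronchospasm, is on none of the lists, which suggests a wider intent. Respiratory outcomes are collected as secondary endpoints, deterioration is monitored, and the DSMB meets after 5 and 25 patients and may stop for safety.

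Much of this stands and rules out stronger readings:

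- A reader might infer that no respiratory event can ever count. The catch-alls and indirect routes prevent that; the supportable statement is that capture is unreliable.
- A reader might infer that deaths from respiratory failure are excluded. The text is contradictory on this, not exclusionary.
- A reader might infer that the protocol expects losartan to worsen the infection. It raises the possibility and argues against it.
- A reader might infer that the data are lost or, conversely, that they are already in hand for every group. They are secondary endpoints, but for historical controls the Control section promises only information relating to safety criteria.

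It is also fair to object that deleting the list altogether could create bias. Open-ended capture would be prospective in treated patients and by chart review in historical controls.

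The reply leaves the gap in place. No source names the event, the routes in depend on judgement, and the secondary endpoints do not feed the rule.

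**Conclusion.** The point holds for non-fatal respiratory deterioration. Taken literally, the AE and SAE definitions leave it out of the only numerical safety criterion except by discretionary or indirect routes, so losartan could meet that criterion while respiratory failure worsens. That this rule serves as the primary safety comparison is an inference: safety is primary, no variable is named, and no other rule is given. For fatal deterioration the finding is narrower: the two SAE statements must be reconciled.

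The size cannot be derived from the documents. The 5 to 10 patients in 50 only illustrate an assumed excess. A reader might infer that the ±20% rule would have caught that excess had it been counted. Under an absolute reading on a pooled patient-level total it would not (6 to 16 points against 20). That is why the remedy has to be a separate comparison and not merely a longer list. The gap should be closed before the safety conclusion is drawn, because it bears on the trial's primary question.

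**What to change.** 1. Keep the AE list, and state that death from any cause during participation counts as an SAE whether or not the underlying event is listed. This reconciles the two SAE statements.
2. Add a second line to the primary safety comparison: new mechanical ventilation, non-invasive or high-flow support, ICU transfer, ECMO, renal replacement and in-hospital death, regardless of attribution. Give the number at risk for each, because patients may already be ventilated at enrolment.
3. Draw the safety conclusion from both lines, not from a pooled total alone. Say in advance how the second line will be judged, since a 20-point absolute margin applied there would also tolerate a 10 to 20 point excess. Do not add the lines together: death and renal events can appear in both.
4. State that these outcomes are extracted from the health record in the same way and over the same time window for treated patients, controls who decline losartan, and historical controls. AE collection currently starts at consent, which retrospective controls do not give, so they need a defined index day.

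Cost: protocol wording, one more table and an added record query for historical controls. The background event count will be higher, because disease progression is counted in every group.
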